# **Clinical Laboratory Evaluations**

Blood and urine samples for safety laboratory assessments will be collected at screening, month 6, and month 12. To the extent possible, blood samples will be obtained at approximately the same time of day and under non-fasting conditions. All safety labs except prolactin will be processed by LabCorp.

Laboratory test results, including prolactin results, will be summarized by treatment and over all participants at each time point for the absolute value itself and for changes from baseline. We will also summarize the percent of participants in each treatment group with values within alarm ranges, which will be defined prior to breaking the blind. The mean value and SD of the labs within alarm ranges will be summarized at each time point. All measurements of the out of range value for each participant with an out of range value will be listed.

# 12-lead Electrocardiogram (ECG)

A 12-lead ECG will be performed at screening, month 6, and month 12. To the extent possible, ECGs will be performed after the participant has rested quietly for at least 5 minutes in the supine position. QT intervals will be automatically corrected by the ECG machine using Bazett's formula (QTcB) and Fridericia's formula (QTcF). It will be noted if the participant was agitated or in a nonsupine position.

Interval data will be summarized at each time point for the absolute value and for changes from baseline by treatment group and over all participants. Intervals that are outside of alarm ranges will be summarized. Overall assessment of ECG as normal or abnormal will also be summarized by treatment group using counts and percentage.

#### Safety Data Reported to the DSMB

- Safety data will be submitted to the independent DSMB three times per year. The following summaries will be provided for review at each meeting:
- Summary table of participant disposition including number screened, number randomized, number completed, percent early terminated, and reasons for early termination.
- Listing of all participants terminating the study early with duration of participation in the study and duration of treatment and reason for study discontinuation.
- Listing of all serious TEAEs.
- Summary table of the number and percent of participants with TEAEs by severity.
- Summary table of the number and percent of participants with TEAEs by relationship to study drug.
- Summary table of the number and percent of participants with TEAEs leading to study early termination.
- Listing of all TEAEs leading to study early termination.
- Summary table of the number and percent of participants with TEAEs by preferred term.
- Summary table of the number and percent of participants with TEAEs by category.
- Listing of all severe TEAEs.
- Summary table of the number and percent of participants with of suicidal ideation or vocalizations, self-injurious behaviors and suicide attempts by treatment group.

- Listing of all suicidal ideation or vocalizations, self-injurious behaviors and suicide attempts by treatment group.
- Summary of the proportion of suicidal ideation or vocalizations, self-injurious behaviors and suicide
  attempts by treatment group that are judged to be more severe than the participant's baseline level
  of such behaviors.
- Additional summaries of other study data, including efficacy data, may be provided if requested by the DSMB.

#### SAMPLE SIZE AND STATISTICAL POWER CONSIDERATION

We will use a mixed longitudinal model for our primary analyses (see Efficacy Analyses section). Since some aspects of the model such as covariance structure are unknown, we performed power and sample size calculations using a more conservative, simplified model corresponding to a two-group t-test on change scores. We plan to analyze two co-primary outcomes measured as change from baseline to month 6: the ABC-SW, which will provide consistency with pivotal trials of other medications hypothesized to improve ASD social symptoms, and the combined social score, which integrates ABC-SW symptoms with the new PDDBI-SV in order to fully capture the range of impairments in reciprocal social behaviors observed in ASD. We will use an alpha of 0.025 to correct for two co-primary outcomes. SOARS-B is powered to allow independent evaluation of oxytocin efficacy in low and high-functioning youth.

ECG	Electrocardiogram
GUID	Global Unique Identifier
FAS	Full Analysis Set Population
IU	International Unit
K	Potassium
LS	Least Squares
OT	(intranasal) Oxytocin
MMRM	Mixed Model with Repeated Measures
Na	Sodium
NIH	National Institutes of Health
PDDBI-SV	Pervasive Developmental Disorders Behavior Inventory – Screening Version
PP	Per-protocol Population
OXTR	Human Oxytocin Receptor Gene
Q1	First Quartile
Q3	Third Quartile
RMET	Reading the Mind in the Eyes Test
SAP	Statistical Analysis Plan
SD	Standard Deviation
SF	Sociability Factor, a combined measure derived from the ABC-SW & PDDBI-SV
SLAES	Systematic Longitudinal Adverse Events Scale
SOARS-B	Study of Oxytocin in ASD to Improve Reciprocal Social Behaviors
SRS-2	Social Responsiveness Scale (version 2)
TEAE	Treatment-Emergent Adverse Event
VABS	Vineland Adaptive Behavior Scales 2 nd edition

#### 1. INTRODUCTION

### 1.1 PURPOSE

The purpose of this SAP is to outline the planned analyses to support the completion of the primary manuscript to be written for the SOARS-B Study. Other analyses not identified or defined in this SAP may be performed to support the clinical trial, and will be described in separate SAPs. Any post-hoc or unplanned analyses performed and not identified in this SAP will be documented in the respective manuscript.

#### 1.2 STUDY OBJECTIVES

#### 1.2.1 PRIMARY OBJECTIVE

 To determine the efficacy of intranasal oxytocin (OT) for the treatment of deficits of reciprocal social behaviors in child or adolescent participants with autism spectrum disorders (ASD) as measured by changes in the Aberrant Behavior Checklist- Social Withdrawal Scale (ABC-SW).

#### 1.2.2 SECONDARY OBJECTIVES

- To determine the efficacy of OT as measured by changes in ABC-SW scores as a function of baseline plasma oxytocin levels, age and functional level and the interaction of each with treatment, and with treatment and week.
- To determine the safety and tolerability of OT in participants with ASD as measured by incidence of treatment emergent adverse events (TEAEs) and abnormal laboratory values, tolerability of OT dose, and time to early termination.
- To determine the efficacy of OT as measured by changes in the sociability factor (SF), a combined measure formed from 13 items of the ABC-SW and the Pervasive Development Disorders Behavior Inventory –Screening Version (PDDBI-SV).
- To determine the efficacy of OT as measured by changes in ABC-SW scores in low-functioning and highfunctioning strata separately.
- To determine the efficacy of OT as measured by changes in Social Responsiveness Scale Version 2 (SRS-2) Social Motivation scores and Stanford Binet-5 Abbreviated IQ standard scores.

### 1.2.3 EXPLORATORY OBJECTIVES

• To determine the efficacy of OT on other clinical assessments including the subscales of the ABC, SRS, Vineland Adaptive Behavior Scale 2nd edition (VABS), and Caregiver Strain Questionnaire, the PDDBI-SV; the Clinical Global Impressions Severity and Improvement scores and, in the high functioning participants only, the Reading the Mind in the Eyes Test (RMET).

#### 1.3 STUDY DESIGN

This is a multicenter, randomized, double-blind, stratified, flexible dose, placebo-controlled study designed to evaluate OT in participants with ASD. OT will be given as an intranasal preparation with two different

[figure not shown]
concentrations of 8 IU per insufflation or 24 IU per insufflation. Oxytocin will be administered daily, in single doses up to 40 IU or divided doses in the morning and early afternoon as described in the protocol. Total daily dose is flexible, between 8 IU and 80 IU per day.

Participants who successfully complete screening and baseline assessments and are deemed eligible will be randomized to OT or placebo treatment in a 1:1 ratio, stratified by age group (3-6, 7-11, 12-17) and functioning (low, high), for a total of 6 strata. Randomization will not be stratified by center, as it was felt that additional stratification by center would lead to too many strata, a loss of degrees of freedom, and the potential for a grossly unequal randomization to treatments.

A schematic representation of the study design is shown in Figure 1. After screening and randomization at week 0 (W0), participants enter a double-blind treatment period of 24 weeks (W24), followed by open-label treatment with OT for 24 weeks, termination of OT at the end of week 48 (W48), and a week 53-55 (W53-55) or week 72 OFF treatment follow-up. Although the study design requires patient follow-up from week 0 to week 53-55, this SAP focuses on data analyses for the double-blind treatment period (week 0 to week 24).

Efficacy, safety, and tolerability are measured every four weeks throughout the treatment period. Participants who terminate early are asked to provide safety data through the remainder of the study. The schedule of assessments is provided in Table 1.

Figure 2: Schematic Representation of the Study Design

\*indicates safety labs and genetic sample taken. Primary outcome assessed at bolded time points.

**Table 1: Schedule of Assessments** 

6.0 Schedule of Events	Scrn	Double Blind Treatment								Open-label Treatment			FU
Procedure		Wo-	I Vv2	T VV4	Vv8	1 VV12	I VV16	Vv20	W24/T	W28	T W36	VV48	W53-55
ADOS-2	1 x			1	1				X'				1
ADLR	TX'								1	1	i	İ	<del>i</del>
Significant Binet/iviulien	X								X		†	İ	<del>1</del>
DSM-V Checklist	İX								1		1	i —	1
Indusion/Exclusion	1X	T X		1							1	i -	1-
Demographics		X											1
Family (viel Hx (iNIH Form)	X								7		1		_
Randomization Form	1	X									İ	İ	1
GUID Acquisition Form/GUID Record	1 -	TX-	1	$\vdash$	+					1	+		1
Con Meds	<del> </del> x	X	_	TX.	X		X	X	X	<del> </del> x	<del> </del> x	X	+
Vital Signs	<del>  X</del>	Î		<del>l x</del>	<del>  x</del>		x	X	1 X	<del>1 x -</del>	<del>†x</del>	X	-1-
Med/Psych History (SLAES)	<del>  x</del> -	<del> </del> $\hat{x}$	-	+^-			<del>  ^ -</del>			+^-	+^-		-
Adverse Effects (SLAES/Suindairty)	<del> </del>   -	<del>  ŷ</del> —		<del>  x</del>	$+_{X}-$	_	-x	+x-	+x-	$+_{X}-$	$+_{X}-$	x-	$+_{x}-$
Full Physical Exam (NIH Form)	<del> </del> â	+^-	-	+^-	+^-	-	 		+^-	+^-	+^-		+^-
Foursed Clinical Physical Exem	+^-	l x	-	<del>l</del> x	+x		X	X	X	+-	1	V	4
	+-	+^-	_	+^-	+^-		^_		^	ΙX	ĮΧ	X	
Medicai History (NIH Fo m)	TX	<del>                                     </del>	-	l -	<del>                                     </del>		$\vdash$	-	-	+-	1		1
CGIS and I	_	Ϋ́	-	X	X		X	X	X	ΙX	IX	X	1
VAS Change (Clinician and Coord)	4	X	-	X	X		Х	X	X	X	ŢΧ	X	4
Social Skills Therapies		X		X	X		X	X	X	ĮΧ	ŢΧ	X	4
Psychosocial Therapies		Х	_	Х	X		Х	X	X	X	ŢΧ	X	
Laboratory	110										1		
ECG	I X								X				
Fernale Reproductive Status	X	X		X	X		Х	X	X	X	X	X	4
Urine/Serum Pregnancy'	X										8		1
Safety labs	IX_								X		X	X	
mRVA sample	TX	X**			X				X		X		
Methylation sample	X	X**			X		Į.		X		IX		
Plasma/salivary oxylocin	IX	X**			X				X		T X		
Whole blood serotonin	TX				X				X				1
Parent Questionnaires						i			Î				
Questioninaire Guidance Form		X		X	X	X	X	X	X	X	TX	X	1
Social Opportunity Questionnaire	4	X		X	X	X	X	X	X	X	TX	X	
ABC		X		X	X	X	X	X	X	X	IX	X	
PDDBLSV		X		X	X	X	X	X	X	X	İΧ	X	1
CASI-5	1 -	X							X	1	+	X	1 -
Carectiver Strain		<del>  x</del>	<del>                                     </del>	1	+				X		+	X	1
Vineland-II (Survey Form)	+	<del>  x                                   </del>							<del>  x</del>		+	<del>  x                                   </del>	+
SRS-2	1	<del>l x</del>	H	1		X			X	1	1x	X	+
Subject Completed Questionnaires	1	1^_							^		1^		
Reading Mind in Eves Test*	1	X			X				X	<del>                                     </del>	1	X	-
Self-Rating of social function	+	₹	_	1	+^				1 î	+	+	<del> </del> x	+
Medication		1^							1			_	
Oxytocin Administration Instructions*	2	X								-			3 /-
	1	<del>  x</del>	X	X		-	X	7	<del> </del> X	-	<del> </del> x -	X	-
SOARS-B Parent Dose Sheer* Risks Handout	1	<del>  x  </del>	^	+^-	X			X		X	+^-		1
	-			-	+-		<del></del>		1 X	1-	+-	-	+-
Medication Compliance		L.,	L	X	X		X	X	X	X	X	X	1 X
Oxytocin Dosing Log (staff)	1	X	ΙX	X	X		X	X	X	X	X	X	T X

0-CGI-S only at baseline, CGI-I and CGI-S at most other time points (office visits)

- 3- Assessment will be obtained only in participants who have fluent phrase speech & can define basic feelings and friendship.
- 4- Completed each time the participant returns study medication
- 5- The appropriate SOARS-B Parent Dose Sheet should be given at each time dose changes to parents
- 6-Stanford Binet or Mullen may be completed at physician discretion
- 7- At physician discretion
- \*Must be given at baseline, but also can be given at any other time during the course of the study at study staff discretion
- \*\*Optional redraw of mRNA, plasma/salivary oxytocin, and methylation at baseline for those who may have had a lengthy time between screening and baseline (not safety labs). Procedures for visits are allowed to be completed on separate days, however, subjects may not be dispensed open label medication until all week 24 procedures are completed

Required at screening but can be done at any time during the course of the study at physician discretion. Must have a negative pregnancy test within two weeks of baseline.2-Safety labs to include: glucose (random), CO2, Cl, K, Na, Creatinine, BUN, AST, ALT, full urinalysis, urine pregnancy in pubertal girls. Screening safety labs must be repeated if more than 12 months between screening and baseline.

#### **2.GENERAL STATISTICAL CONSIDERATIONS**

## 2.1 Analysis Populations

In all populations, participants will be analysed in the treatment group into which they were originally randomized. Measurements from participants excluded from the pre-defined analysis populations or extra measurements (such as unscheduled or repeat assessments) will not be included in summary tables or figures unless specified otherwise.

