#### **5.4 Clinical Laboratory Evaluations**

Blood and urine samples for safety laboratory assessments will be collected at screening, and week 24. To the extent possible, blood samples will be obtained at approximately the same time of day and under non-fasting conditions. All safety labs will be processed by LabCorp.

Laboratory test results, including prolactin results, will be summarized by treatment at baseline and for changes from baseline. We will also summarize the percent of participants in each treatment group with values within alarm ranges, which will be defined prior to breaking the blind. The mean value and SD of the labs within alarm ranges will be summarized at each time point. All measurements within alarm ranges for each affected participant will be listed.

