#### 5.5 12-lead Electrocardiogram (ECG)

A 12-lead ECG will be performed at screening, and week 24.

Interval data will be summarized at baseline and week 24 for the absolute value and for changes from baseline by treatment group. Intervals that are within alarm ranges will be summarized and listed by participant. Overall assessment of ECG as normal or abnormal will also be summarized by treatment group using counts and percentages.

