#### 6.6 Unscheduled Visit or Re-Evaluation Visit

Subjects may be asked to come in for an unscheduled visit at any time during the course of the study if the treating physician feels it is necessary to see the subject in person or to complete a PK visit. Subjects will be instructed to contact the site between scheduled visits if there are any issues that need to be addressed.

Subjects may also be re-evaluated with appropriate assessments completed for any of the following reasons:

- If the subject's dose is mandatorily reduced, then these assessments should be completed 2-4 weeks after the dose has been reduced.
- If the subject has had a CGI-I score of 6 or 7, then the assessments should be completed two-four weeks later at physician discretion.

During these visits, all efforts should be made to obtain the following assessments:

- Vital signs (only if in person visit)
- Review of concomitant medications
- SLAES (adverse events) and suicidality assessment
- CGI-S and CGI-I
- Focused Clinical Physical Exam (only if in person visit)
- If physician feels it is indicated, safety labs or ECG may be obtained.

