## **8.1.1** Treatment Emergent Adverse Events

In this trial we are documenting all AE's, but analysis will focus only on Treatment Emergent AE's (TEAE's). Medical and behavioral conditions that are present at screening and/or baseline will only be considered treatment emergent adverse events if their severity increases significantly after the participant has taken at least one dose of study treatment. Intermittent conditions such as seasonal allergies will only be considered TEAEs, if the severity or frequency is significantly greater than in the previous two years. Only TEAEs will be considered in the adverse event safety analyses.

If a TEAE occurs, its relationship to study product (assessed only by those with the training and authority to make a diagnosis, which would include MD, DDS, DMD, PA, Nurse, Nurse Practitioner or DO), and resolution/stabilization will be coded at the resolution of the event or end of the subject's participation in the study. All TEAEs occurring while on study must be documented appropriately regardless of relationship. All TEAEs will be followed to adequate resolution. If a TEAE is a severe adverse event rating (3) and an Unexpected Problem (UP-no prior history of issue/not commonly seen in autistic patients and not described as a risk of the treatment), the UP form must be completed. If a TEAE is an SAE the the SAE form and SLAES (unscheduled visit) must be completed.

**Severity of Event:** All AEs will be assessed by the clinician using a protocol defined grading system. For events not included in the protocol defined grading system, the following guidelines will be used to quantify intensity.

- **Mild:** events require minimal or no treatment and do not interfere with the subject's daily activities.
- **Moderate:** events result in a low level of inconvenience or concern with the therapeutic measures. Moderate events may cause some interference with functioning.
- **Severe:** events interrupt a subject's usual daily activity and may require systemic drug therapy or other treatment. Severe events are usually incapacitating.
- Life-threatening: Substantial risk dying or requires intervention to prevent death
- Death related to AE: Subject died as a result of the event, self-explanatory

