#### 8.6.4 Cardiac Monitoring Plan

Based on the patient's age, gender, and height percentile, we have adapted blood pressure parameters where blood pressures above or below the set threshold will prompt the PI to consider doing an EKG. These parameters were derived from the National High Blood Pressure Education Program Working Group on High Blood Pressure in Children and Adolescents(Falkner, Daniels et al. 2004). We have likewise adapted parameters from Pediatric cardiology for practitioners(Park 2008) and Normal ECG standards for infants and children (Davignon, Rautaharju et al. 1979)to establish heart rate guidelines where patients whose heart rate is above or below these thresholds will be considered for an EKG at every visit. Finally, we will incorporate clinical signs and symptoms of cardiac risk into our assessment with the vital sign measurement and specifically query for the presence of syncope, dizziness, palpitations, shortness of breath, and bradycardia or tachycardia. The clinical parameters will be incorporated into the SLAES. The specific parameters for heart rate, blood pressure are located in Appendix A. We believe, given the low cardiac risk of oxytocin, that careful monitoring of vital signs and clinical signs and symptoms at every visit will be adequate to ensure the safety of our patients.

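### SAP 2.1 by default keeps unscheduled ECGs, labs and vital signs out of summary tables, and the safety sections state no exception for the by-arm alarm summaries

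*Combined protocol and SAP*

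**What the plan says.** SAP v2.0, section 2.1, sits under the general statistical considerations and so governs every analysis in the SAP. It states that "extra measurements (such as unscheduled or repeat assessments) will not be included in summary tables or figures unless specified otherwise". The last three words allow exceptions.

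The safety sections set out what is measured and what is tabulated:

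- SAP 5.4 on labs: "Blood and urine samples for safety laboratory assessments will be collected at screening, and week 24". By arm, it will summarise the "percent of participants in each treatment group with values within alarm ranges". It also lists every alarm-range lab measurement by participant.
- SAP 5.5 on ECG: "A 12-lead ECG will be performed at screening, and week 24". Interval data are summarised at baseline and week 24. Alarm-range intervals are summarised and listed by participant, and the overall normal/abnormal reading is counted by arm.
- SAP 5.2 on vital signs: the percentage in the alarm range is given by arm at each time point.

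Protocol v6.0 provides for further measurements. Under the cardiac monitoring plan (8.6.4), "blood pressures above or below the set threshold will prompt the PI to consider doing an EKG", and participants whose "heart rate is above or below these thresholds will be considered for an EKG at every visit". At an unscheduled or re-evaluation visit (6.6), "If physician feels it is indicated, safety labs or ECG may be obtained". The early termination list (6.5) contains neither an ECG nor labs.

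**The concern.** Specific Aim 2 of the protocol is safety and tolerability. Its Analysis 2a compares clinically significant lab and ECG changes between the arms across the whole 24 weeks. The SAP schedules one post-dose ECG and one post-dose lab draw in that period, at its end. Any earlier value exists because something prompted it, so these are the values most likely to be abnormal. A general rule that removes them from tables turns a 24-week comparison into a week-24 comparison.

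Two kinds of participant are affected. One has an abnormality that is seen early and has resolved by week 24. The other stops early and has no scheduled post-dose ECG or lab, so an unscheduled value may be the only one.

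**Working it through.** The plan gives no figure to reproduce. The check sets the rule beside each safety section and looks for text that specifies otherwise.

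| Domain | Scheduled post-dose, blinded phase | Extra measurements under the protocol | By-arm alarm summary | Listing |
|---|---|---|---|---|
| Vital signs (SAP 5.2) | Weeks 4, 8, 16, 20, 24 | In-person unscheduled or re-evaluation visits (6.6) | Percentage per time point | On request |
| Safety labs (SAP 5.4) | Week 24 | Physician-indicated (6.6) | Percentage of participants, no visit stated; mean and SD per time point | All alarm-range values |
| ECG (SAP 5.5) | Week 24 | Vital-sign prompts (8.6.4); physician-indicated (6.6) | Alarm-range intervals and normal/abnormal counts, no visit stated | Alarm-range intervals |

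**Step 1: is there an exception?** None of the three sections says that unscheduled or repeat values enter a table. The lab percentage and the ECG alarm summary name no visit. That leaves them open, but leaving the visit unstated does not specify an exception, so the default in 2.1 applies. Two programmers could reasonably produce different percentages from the same data.

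**Step 2: do other outputs give the arm comparison?**

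- The listings fall outside the rule, so alarm-range lab values and ECG intervals remain visible, but participant by participant and not as arm percentages.
- SAP 5.1 monitors adverse events continuously to week 24 and tabulates TEAEs by arm, so a clinical event behind a prompted test can appear there. For labs this route is incomplete, because the adverse event definition in protocol 8.1 covers an abnormal lab only when it was not obtained directly for the study.
- Alert values under protocol 8.2.5 go to the coordinating center, which is reporting and not an arm comparison.
- The standing DSMB list in SAP 5.6 contains no lab, ECG or vital-sign summary.

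**Step 3: how many ECGs could be involved?** The final sample size is 290 (SAP section 6). Post-baseline blinded visits with vital signs are weeks 4, 8, 16, 20 and 24; week 12 is questionnaires only. Week 24 already has a scheduled ECG, so four visits can generate an extra one:

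- 4 x 290 = 1,160 visits, if every participant attends all four.
- At an assumed 1%: 0.01 x 1,160 = 11.6, about 12 ECGs.
- At an assumed 5%: 0.05 x 1,160 = 58 ECGs.

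For comparison, there can be at most 290 scheduled week-24 ECGs, so the range is about 4% (11.6/290) to 20% (58/290) of that number. ECGs and labs at unscheduled visits would add to it. The documents give no rate for either.

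**The case against.** The strongest reply is that 2.1 is only a default. SAP 2.1.1 mentions table shells, which are not among the documents, and a shell might supply the exception. The alarm summaries in 5.4 and 5.5 are not tied to scheduled visits. This stands to the extent that a reader who inferred an absolute bar on unscheduled values would go beyond the text. It does not show that the values are included.

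A reader might also infer that prompted findings vanish from the safety results altogether. The documents do not support that: the ECG and lab listings, the by-arm TEAE and SAE summaries and the week-24 assessment all remain.

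A further tempting inference is that the rule removes adverse event records taken at unscheduled visits, since protocol 8.1.1 says that for an SAE the "SAE form and SLAES (unscheduled visit) must be completed". SAP 5.1 answers this: adverse events are monitored continuously and SAEs are expressly listed and summarised by arm. That specific text prevails over a general rule about extra measurements.

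Finally, week-24 prevalence on a common schedule is a legitimate comparison, and discretionary testing can differ in frequency between arms. That is a good reason to keep the by-visit tables and to show how often each arm was tested. It is not a reason to have no by-arm count of abnormalities at any time. The tables are descriptive, and the overall stopping test in protocol 8.6.3 uses severe and life-threatening or fatal adverse events, so that test is not affected.

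**Conclusion.** The point holds as a gap with a stated default. Followed as written, SAP 2.1 leaves prompted and clinically indicated ECGs, labs and vital signs out of the by-arm summaries, and 5.2, 5.4 and 5.5 state no exception. For the lab and ECG alarm summaries the kindest reading is that the plan is ambiguous. What is lost is early or transient abnormality from the arm comparison that Analysis 2a calls for.

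The size is unknown. The range of about 12 to 58 ECGs rests on an assumed 1% to 5% of 1,160 visits with full attendance, and the protocol only asks the investigator to consider an ECG. A reader might infer that a difference between the arms would be hidden. The documents cannot show that, because they give neither the number of prompted tests nor their split by arm. The change is worth making because it is cheap and the affected values are the informative ones.

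**What to change.** In SAP 2.1, limit the exclusion of unscheduled and repeat measurements to efficacy summaries and by-visit summaries.

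In SAP 5.2, 5.4 and 5.5, keep the by-visit tables and add one line per parameter: the number and percentage of participants in each arm with any alarm-range value after the first dose and before open-label drug, whether scheduled, repeat, unscheduled or from early termination. Do the same for an ECG read as abnormal. Give the number of participants with at least one post-dose measurement as the denominator.

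Participants tested more often have more chances of an alarm value, so show the number of measurements by arm beside each percentage.

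The cost is a few sentences of SAP text and one added table per domain. It needs no new assessment and no change to clinical procedures, because it uses measurements already provided for in the protocol.
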